## 9.5. Handling of Missing Data

Every effort will be made to obtain complete data. Data analysis will be based on collected data. Missing data will not be imputed using any imputation methods. Missing data is not expected for blood pressure values because up to 15 blood pressure determination procedures will be allowed, if necessary, to obtain 10 blood pressure recordings, thus minimizing the likelihood of missing data in IBP and NIBP blood pressure determination pairs. Any pair of blood pressure measurements with a missing value will be excluded from analysis.

## 9.6. Pass/Fail Criteria of the Study

The study will be considered to pass if a sufficient data set is collected to satisfy the requirements of ISO 81060-2:2013.

## 10. DEVIATIONS

### 10.1. Management of Protocol Deviations

Deviations to the protocol may occur when necessary to protect the life or physical well-being of a patient. Except in an emergency, prior approval by the Sponsor is required for changes in, or planned deviations from this protocol. If these changes affect the scientific soundness or the safety and welfare of the patient, prior EC/IRB approval is also required. Planned Protocol Deviation documentation must be filed in the Site Study Regulatory Binder.

There are two types of unplanned protocol deviations, critical deviations and non-critical deviations. All deviations must be documented and reported, the criticality of the deviation will determine the reporting path.

**Critical Deviations:** Deviations that significantly affect the safety, efficacy, integrity or conduct of the study. These deviations must be reported to the Sponsor no later than 5 working days from awareness of occurrence and reported to the EC/IRB per the deviation reporting policy.

If an Investigator uses a device without obtaining informed consent, the Investigator shall consider this a critical deviation and report the event to the Sponsor and the EC/IRB within 5 working days of the occurrence

**Non-Critical Deviations:** Protocol deviations that DO NOT significantly affect the safety, efficacy, integrity or conduct of the trial. These deviations must be documented on the Case Report Form Protocol Deviation page and will be reviewed by the study monitor.

## 11. COMPLAINT HANDLING AND ADVERSE EVENT REPORTING

### 11.1. Foreseeable Adverse Events and Device Effects

The study procedure requires adding NIBP measurements to a patient's procedure. While NIBP is non-invasive, there are some foreseeable risks associated with NIBP, as follows:

- slight discomfort upon inflation of the cuff,
- possible bruising,
- petechial rash

- discoloration of the skin beneath the cuff
- peripheral nerve injuries
- skin avulsion
- compartment syndrome
- ischemia

Whether or not the patient participates in the study, there are risks to having indwelling monitoring lines placed or having non-emergent aortic catheterization procedures with or without general anesthesia. To protect neonatal subjects, only subjects with existing indwelling monitoring lines will be enrolled, and no indwelling lines will be placed for study purposes. Foreseeable risks associated with these invasive procedures, as required for IBP, include:

- Bruising
- Bleeding
- Heart attack
- Stroke
- Damage to the artery where the catheter was inserted that may require additional attention (pseudoaneurysm), including shear damage
- Irregular heart rhythms (arrhythmias)
- Allergic reactions to the dye or medication
- Tearing the tissue of your heart or artery
- Kidney damage
- Infection
- Blood clots
- Ischemia
- Air embolism
- Potentially serious reactions to prescribed general anesthesia and/or sedatives

While general anesthesia is not a requirement of this study, it is foreseeable that some patients undergoing aortic catheterization procedures will be incidentally administered prescribed general anesthesia and/or other sedatives during the study. Though general anesthesia is widely considered safe for routine clinical use, it is known to be a potent neuromodulator with potentially serious documented side effects. This research involves extension of the procedure by approximately 25 minutes to collect data, which may incidentally extend prescribed anesthesia and/or other medication administration. Though no definitive cumulative or long-term effects of general anesthesia are known with certainty, to mitigate against these possible risks the study will not enroll subjects that have history of repeated recent anesthesia, and no subject will be allowed to participate more than once in the study. The risks associated with general anesthesia during this study are not expected to be significantly higher than those that the subject would have otherwise been exposed to had he or she not participated in this research.

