### **2.3.3. General Controls and Risk Mitigations (all subjects)**

No medicinal agents, including anesthesia and sedatives, are specifically required by the study; however, being in the study will not prevent subjects from receiving medications that are otherwise prescribed for their procedure. Extension of administration of general anesthesia consisting of approximately 25 minutes is foreseeable. Because repeat anesthesia administration has been identified as a central risk factor, particularly amongst pediatric subjects, the study will not enroll any subject aged greater than 29 days but less than 12 years of age that has recently received anesthesia outside of the study within the last 3 months. Additionally, no subject will be allowed to participate more than once to mitigate any possible risks associated with repeat anesthesia administrations.

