### 6.3. Number of Subjects

The total minimum enrollment for the two study arms is 83 total evaluable patients (maximum of 200 patients), as follows:

1. **PDM-SuperSTAT Arm ( $N_{PDM}$ ):** 45 evaluable patients with GE DINAMAP® SuperSTAT algorithm (PDM Module) on CARESCAPE Monitor B650, to achieve a total target of  $\geq 150$  BP data pairs in patients  $\geq 3$  years old (up to 10 paired measurements per subject) and  $\geq 150$  BP data pairs in patients  $< 3$  years old (as described in Table 2).
2. **PSM-Datex-Ohmeda Arm ( $N_{PSM}$ ):** 29 evaluable patients with Datex-Ohmeda algorithm (PSM module) on CARESCAPE Monitor B650, to achieve a total of  $\geq 150$  BP data pairs in patients  $\geq 3$  years old (up to 10 paired measurements per subject) and  $\geq 150$  BP data pairs in patients  $< 3$  years old (as described in Table 2).

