## 6.5. Exclusion Criteria

Subjects will be excluded that:

1. Have previously participated in this study (no subject may participate more than once).
2. Exhibit signs or symptoms or have a current diagnosis of peripheral vascular disease in upper AND/OR lower limbs;
3. Have current, uncontrolled circulatory shock;
4. Exhibit injuries, deformities, intravenous lines, or other abnormalities that, in the opinion of the investigator, may prevent proper cuff application or functioning;
5. For women of child-bearing potential, are currently pregnant, suspected to be pregnant, or are currently lactating;
6. Have any condition that could interfere with the subjects ability to tolerate the procedure, including having a maximum of 4 fast flushes (adult, adolescent, or pediatric patients aged >29 days) or 1 fast flush (neonates aged <29 days);
7. If aged greater than 29 days but less than 12 years of age, have previously had any clinical or research procedure requiring general anesthesia in the last 3 month period;
8. If aged greater than 29 days but less than 12 years of age, are expected to require more than three (3) total hours of continuous general anesthesia for the scheduled procedure (including clinically necessary anesthesia and anticipated 25 minute extension for study purposes).

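### Section 11.1 states an anesthesia-history exclusion with no age limit, but the only criterion that applies it stops at 12 years, so the 37 patients over 12 required by Table 1 fall outside it

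*Combined protocol and SAP*

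**What the plan says.** Three current sections of the protocol address recent anesthesia.

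- **Section 11.1** notes that the research extends the procedure by about 25 minutes and may incidentally extend prescribed anesthesia. It offers two mitigations: "the study will not enroll subjects that have history of repeated recent anesthesia", and single participation. It then concludes that anesthesia risk is not expected to be significantly higher than it would be outside the study.
- **Section 6.5, item 7** is the eligibility rule: "If aged greater than 29 days but less than 12 years of age, have previously had any clinical or research procedure requiring general anesthesia", with a look-back of 3 months.
- **Section 2.3.3** says that "the study will not enroll any subject aged greater than 29 days but less than 12 years of age that has recently received anesthesia" and adds "that has recently received anesthesia outside of the study within the last 3 months". Its heading refers to all subjects, but this sentence is age-limited. The reason given is "Because repeat anesthesia administration has been identified as a central risk factor, particularly amongst pediatric subjects".

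One mitigation does apply at every age, Section 6.5 item 1: "Have previously participated in this study (no subject may participate more than once".

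On numbers, Section 6.3 says "The total minimum enrollment for the two study arms is 83 total evaluable patients" and then gives arm minima of 45 and 29. Table 1 sets out the strata.

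**The concern.** Someone judging subject protection from Section 11.1 alone would conclude that nobody with repeated recent anesthesia can enter the study. A site applying Section 6.5 would enroll a 13-year-old or an adult with several recent general anesthetics, provided no other criterion applied. One of the two mitigations offered for study-added anesthesia time is then missing from the eligibility rules for everyone over 12. Adolescents are the most exposed case, because Section 6.2 lists them among the vulnerable subjects and Section 2.3.2 foresees the 25-minute extension in catheterized patients of all ages above 29 days.

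What is at stake is the accuracy of a subject-protection statement. The accuracy endpoints, the sample size and the analysis are not affected.

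**Working it through.** **1. The three statements side by side**

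| | 11.1 | 6.5 item 7 | 2.3.3 |
|---|---|---|---|
| Age range | none stated | >29 days to <12 years | >29 days to <12 years |
| Time window | recent, undefined | 3 months | 3 months |
| Exposure count | repeated | any one | any one |
| Type | anesthesia | general anesthesia | anesthesia |

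Sections 6.5 and 2.3.3 agree on age, window and exposure count. They differ only in general anesthesia against anesthesia. Section 11.1 is broader on age and, read literally, narrower on exposure. No other criterion in 6.5 is based on previous anesthesia.

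**2. The plan's own denominator**

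Inputs are the Table 1 stratum minima.

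- PDM arm: 15 + 7 + 5 + 18 = 45, which matches Section 6.3.
- PSM arm: 15 + 5 + 9 = 29, which matches Section 6.3.
- Sum: 45 + 29 = 74, against the stated minimum of 83. The stated figure does not reproduce; the gap is 9.
- 83 equals 45 + 38. Appendix E records 38 as the superseded PSM number.

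Both denominators are therefore shown below. Section 5.2 allows enrollment without regard to quota once the quotas are met, so the 9 patients between 74 and 83 have no set age.

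**3. Patients certain to be outside the age window**

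These are the strata over 12 years: 15 (PDM general) + 7 (PDM chronic atrial fibrillation) + 15 (PSM general) = 37.

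- 37 / 74 = 50.0%
- 37 / 83 = 44.6%

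**4. Patients certain to be inside the window**

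- Pediatric strata: 5 + 5 = 10.
- Age-defined strata under 3 years: 3 + 3 in PDM and 3 + 3 in PSM = 12.
- Total: 22, which is 22 / 74 = 29.7% or 22 / 83 = 26.5%.

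**5. Patients whose position Table 1 leaves open**

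74 − 37 − 22 = 15. These are 9 in the three PDM weight-defined strata, 3 PDM places under 3 years not tied to a sub-stratum (18 − 15), and 3 in the PSM stratum without an age requirement. Table 1 lets the no-age strata run from birth to under 3 years, so any of the 15 may be on either side of 29 days. On the base of 74, the number inside the rule can be from 22 to 37 (29.7% to 50.0%).

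**The case against.** The best defense is that the age limit is deliberate and only 11.1 is loosely worded. Section 2.3.3 ties the risk mainly to children, and the titles of most references cited in 11.1 for anesthesia effects concern developing brains, neonates or children. Sections 2.3.3 and 6.5 give sites one nearly uniform rule. Within the covered ages that rule is at least as strict as 11.1, since one anesthetic in 3 months is enough to exclude. Item 1 (single participation) and item 6 (any condition interfering with tolerance of the procedure) apply at all ages. Item 8 caps expected anesthesia time in the same pediatric band. Relevant medical history is recorded for everyone under Section 7.2.1. This all stands, and it makes a missing qualifier in 11.1 a plausible explanation. It does not remove the mismatch: recording history excludes nobody, and none of the other criteria carries out what 11.1 says for patients over 12.

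A reader might infer several stronger things that the documents do not support.

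- *At least half of the minimum enrollment is outside the rule.* This is exactly 50.0% on 74, but 44.6% on the stated 83. Passing half of 83 would need at least 5 more patients outside the window, which Table 1 does not require.
- *These patients are not screened for the central risk.* Section 2.3.3 qualifies that risk as mainly pediatric, and single participation covers every age.
- *The 11.1 wording would reach all 74 patients.* Its paragraph concerns aortic catheterization. Subjects aged 29 days or less are studied on lines placed for clinical care, so counting them is doubtful.
- *There are three different rules.* In substance there are two. The difference between anesthesia and general anesthesia is secondary and may be shorthand, because the sentences around it in 2.3.3 discuss general anesthesia.
- *The risk conclusion in 11.1 depends on the exclusion.* The conclusion follows the mitigation in the text, but it compares each subject with the anesthesia he or she would have had anyway. Dependence is not stated.

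**Conclusion.** The point holds as a contradiction between a stated protection and the eligibility criteria. Section 11.1 describes an exclusion without age limit or time window, and Section 6.5 item 7 applies one only from more than 29 days to under 12 years. At the Table 1 minima, 37 patients are certain to be outside the operative rule: 50.0% of 74, or 44.6% of 83. The count rests on the stratum minima alone and leaves out subjects aged 29 days or less.

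The 37 is a count of patients outside the rule, not of patients exposed. Section 11.1 says only that some patients will receive anesthesia or sedatives, and Section 2.3.2 calls general anesthesia typical for pediatric catheterization without saying the same of adults. How many of the 37 would receive study-extended anesthesia cannot be known from the documents.

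**What to change.** Reconcile Sections 2.3.3, 6.5 item 7 and 11.1 so that one age range, one trigger (type of anesthesia, and any or repeated exposure) and one time window appear in all three. Make the mitigation and the risk statement in 11.1 describe only the subjects whom the eligibility rule covers. Which rule is right is for the sponsor and investigators to decide. In the same amendment, settle the minimum enrollment of 83 against the arm minima of 45 and 29.

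The cost is amended wording in those three sections, plus the enrollment figure in Section 6.3, with the usual ethics review. The anesthesia wording changes no sample size, endpoint or analysis. If the sponsor decided to change who is covered, screening could draw on the medical history already collected, and the number of patients excluded would change by an amount the documents do not allow us to estimate.

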## 11.2. Adverse Event Definitions

**Adverse Event (AE):** As defined by EN ISO 14155-2011: any untoward medical occurrence, unintended disease or injury, or untoward clinical signs (including abnormal laboratory findings) in subjects, users or other persons, whether or not related to the investigational medical device.

**Serious Adverse Event (SAE):** As defined by EN ISO 14155 – 2011: an adverse event that

- (a) led to death;
- (b) led to a serious deterioration in the health of the subject, that either resulted in:
  - (1) a life-threatening illness or injury, or
  - (2) a permanent impairment of a body structure or a body function, or
  - (3) in-patient or prolonged hospitalization, or
  - (4) medical or surgical intervention to prevent life-threatening illness or injury or permanent impairment to body structure or a body function;
- (c) led to fetal distress, fetal death or a congenital abnormality or birth defect.

**Anticipated:** Any adverse event and/or reaction, the specificity or severity of which is consistent with the EC/IRB approved informed consent, protocol, investigator brochure, or product labeling.

**Unanticipated adverse device effect (UADE):** As defined by 21 CFR 812.3: means any serious adverse effect on health or safety or any life-threatening problem or death caused by, or associated with, a device, if that effect, problem, or death was not previously identified in nature, severity, or degree of incidence in the investigational plan or application (including a supplementary plan or application), or any other unanticipated serious problem associated with a device that relates to the rights, safety, or welfare of subjects.

## 11.3. Management of Adverse Event Reporting

Any adverse events will be recorded in the subjects study record and the Adverse Event Case Report Form. The following information should be obtained:

- Description of Event
- Date of onset and resolution
- Intensity (mild, moderate, severe)
  - **Mild:** Symptom(s) barely noticeable to the subject or does not make the subject uncomfortable. The AE does not influence performance or functioning. Prescription drugs are not ordinarily needed for relief of symptom(s).
  - **Moderate:** Symptom(s) of a sufficient severity to make the subject uncomfortable. Performance of daily activities is influenced. Treatment of symptom(s) may be needed.
  - **Severe:** Symptom(s) of a sufficient severity to cause the subject severe discomfort. Treatment for symptom(s) may be given.

- Serious (yes/no)
- Relationship to device (unrelated, possibly related, probably related)
  - **Unrelated:** The adverse event is reasonably expected to be related to (or caused by) a concurrent illness, effect of another device/drug or other cause, and is unlikely related to the investigational product
  - **Possibly related:** The adverse event is reasonably expected to be related to the investigational product, and an alternative etiology is equally or less likely compared to the potential relationship to investigational product
  - **Probably related:** There is a strong relationship to investigational product, or recurs on re-challenge, and another etiology is unlikely, or there is no other reasonable medical explanation for the event.
- Treatment given and/or action taken (procedure stopped, withdrawn from study, no action)
- Anticipated (yes/no)

Adverse events will be reported to the local EC/IRB per their policy.

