## 2.3. Device Risk Analysis

Participation in this study has no direct benefit to participants; however, participants may benefit from more reliable assessment of blood pressure readings during their procedure due to the use of multiple devices and multiple recordings for blood pressure measurement. The NIBP device does not pose additional risks to patients, but there are risks associated with the additional IBP comparator procedures above the required clinical care for participating subjects. Use of existing indwelling lines in very young patients is designed to minimize additional disruption of care in pediatric patients.

The NIBP measurement (PDM-SuperSTAT and PSM-Datex-Ohmeda) devices and all patient monitors used in this study under study are commercially available, and all devices will be used according to their labeling. The GxP-validated GEHC PDM Data Collection Module may, when possible, be used to enable digital export of research data typically displayed on patient monitors.. The GxP-validated GEHC PDM Data Collection module works in the same way as the commercially available PDM module, but also has software to enable digital export of the data for research use. The validated non-commercial DC-EDIT and DC-COLLECTOR equipment for the DASH® 4000 and GEHC PDM Data Collection Module serve as a data output connections only and are not expected to impact the clinical function of the device. Participation in this study is not expected to impact patient management, clinical diagnosis, or treatment strategy compared to that which would be determined by the standard of care outside of this study.

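### Adverse events are rated for relationship to the device only, so harm from study-added anesthesia time or IBP procedures cannot be attributed to study participation

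*Combined protocol and SAP*

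**What the plan says.** Section 11.3 lists seven items for each adverse event: description, dates, intensity, seriousness, relationship, treatment or action, and whether anticipated. The only causality item is "Relationship to device (unrelated, possibly related, probably related)". An event is *Unrelated* when "The adverse event is reasonably expected to be related to (or caused by) a concurrent illness, effect of another device/drug or other cause" explains it and the product link is unlikely. *Possibly related* requires that "an alternative etiology is equally or less likely compared to the potential relationship to investigational product". *Probably related* requires, in essence, a strong link with no likely alternative.

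Intensity starts from what the subject perceives. Mild is "Symptom(s) barely noticeable to the subject or does not make the subject uncomfortable" and severe is "Symptom(s) of a sufficient severity to cause the subject severe discomfort".

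Elsewhere the protocol says where participation adds risk. Section 2.3 states that the NIBP device adds none, but that "there are risks associated with the additional IBP comparator procedures above the required clinical care for participating subjects". Section 11.1 states: "This research involves extension of the procedure by approximately 25 minutes to collect data, which may incidentally extend prescribed anesthesia". Sections 2.3.2 and 2.3.3 give the same 25 minutes, and exclusion 8 in Section 6.5 counts it towards a three-hour anesthesia limit. Section 7.2.3 requires dynamic calibration by fast flush (at most one below 29 days of age, at most four from 29 days), and exclusion 6 concerns tolerance of those flushes.

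**The concern.** The form asks about the source that the protocol calls free of added risk, and does not ask about the sources that it names as adding risk. Someone reading the finished safety record could count device-related events, but could not separate events caused by being in the study from events that belong to the underlying catheterization or illness. That separation matters here: the subjects include neonates and children, and Section 11.1 expects anesthesia risk to be not significantly higher than it would have been outside the study. Procedure attribution is the information against which that expectation could be looked at.

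The scale gap and the intensity wording are further weaknesses of the same section. They do not cause the *Unrelated* coding, and each needs its own repair.

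**Working it through.** No arithmetic applies, and the plan states no figure to reproduce. The check sets the definitions against the study-added exposures and then tests whether the levels cover every case.

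**Step 1: study-added exposures against the causality item (Sections 2.3, 3.1.3, 3.5, 7.2.3, 11.1, 11.3)**

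| Exposure added by the study | Coding under Section 11.3 |
|---|---|
| Repeated cuff inflation | Can be rated, since the cuff belongs to the NIBP system under study |
| Extended anesthesia, about 25 minutes | *Unrelated*: it is the effect of a drug, and a link to the NIBP device is unlikely, although the study caused the extra exposure |
| Fast flush | Ambiguous (see below) |

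The flush acts on catheters and transducers that the site selects and supplies (Section 3.5), which points to *Unrelated*. But the DASH 4000 with its data tools is called investigational and is connected to the patient through a fluid-filled catheter and transducer (Section 3.1.3), and the Synopsis calls all aspects of the study investigational. The scale refers to the investigational product without defining it, so investigators at the three sites could code the same event differently.

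**Step 2: are the levels exhaustive?** Take each combination of the device link and the alternative cause.

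| Device link | Alternative cause | Level |
|---|---|---|
| Unlikely | Reasonably expected | *Unrelated* |
| Not unlikely | Equally or less likely than the device | *Possibly related* |
| Strong | Unlikely | *Probably related* |
| Not unlikely | More likely than the device | None |

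The last row fails *Unrelated*, which needs "effect of another device/drug or other cause, and is unlikely related to the investigational product". It also fails *Possibly related*, which needs the alternative to be no likelier than the product. The case is realistic. Section 11.1 lists ischemia and bruising as foreseeable both for the cuff and for the invasive procedure, so limb ischemia in a subject with a cuff and an arterial line can fall in this row. There is also some overlap: a less likely alternative can be an unlikely one, so the second and third rows are not cleanly separated.

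**Step 3: intensity.** Section 11.2 counts untoward clinical signs as adverse events, and Section 11.1 lists skin avulsion and compartment syndrome. The grades offer these anchors:

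- Mild: noticeability, discomfort, performance or functioning, need for prescription drugs.
- Moderate: discomfort, daily activities, possible need for treatment.
- Severe: severe discomfort, treatment possibly given.

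No grade uses a clinical sign, and the severe grade has no functional criterion. The treatment wording hardly separates moderate from severe. Neonates cannot report discomfort, and Section 2.3.2 says that general anesthesia is typical in pediatric catheterization.

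**The case against.** The strongest reply is that nothing is hidden. Section 11.2 defines adverse events whether or not they are related to the device. Section 11.3 records a description, dates, treatment and action taken for each one. Section 11.4 sends every serious event to the sponsor in writing within 72 hours, and deaths also by telephone within 24 hours, with no filter on relatedness. This stands. A reader might infer that the record cannot show harm from the added exposures; the documents do not support that, because only the coded attribution is missing.

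A reader might also infer that the termination decision depends on the causality code. It does not: Section 12.1 lets the sponsor stop for unreasonable risk from unanticipated events or for any other reason. Section 9 plans no analysis by relatedness, and Section 4.3 lists no safety endpoint.

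Nor can it be said that flush events are *Unrelated* by definition. Step 1 shows that they are ambiguous; only the anesthesia case is clear.

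On intensity, mild and moderate contain function and treatment wording that an observer can partly judge, anesthetized subjects may report later, and the gravest outcomes are caught by the outcome-based definition of a serious event. The scale is a poor fit for these subjects, not unusable.

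Finally, the adverse event CRF and the separate serious-event notification form are not in the documents and might ask about procedures. A form for serious events would still leave non-serious events uncovered, and Section 11.3, which sets out what should be obtained, does not ask.

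**Conclusion.** The concern holds as an attribution defect. Section 11.3 rates causality against the device alone, while the protocol locates the added risk in the IBP comparator procedures and in about 25 minutes of extra procedure or anesthesia time. A complication of the extended anesthesia would be coded *Unrelated*, a flush-related event could be coded either way, and neither can be attributed to study participation. Separately, the causality scale leaves one realistic combination without a level. Also separately, the intensity grades lean on felt symptoms in a population where many subjects cannot report them.

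The size is qualitative and moderate. No endpoint, decision rule or reporting duty depends on the code, but the repair is cheap and the present wording miscodes or cannot code events that participation may cause. The conclusion assumes that the CRF follows the Section 11.3 list, and that fast flushes are among the comparator procedures that Section 2.3 has in mind, since that section does not itemize them.

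**What to change.** In Section 11.3 and on the adverse event CRF:

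1. Add a field for relationship to study procedures, naming fast flush or other IBP comparator procedure, study-related extension of the procedure or anesthesia, and repeated cuff inflation, with the same levels as the device field. State what the investigational product is for the device field.
2. Reword the levels so that every event fits exactly one. For example, *Unrelated* turns only on the link being unlikely, and *Possibly related* covers any event whose link is not unlikely and which does not meet *Probably related*. Other wording would serve if it closes the gap.
3. Add observer-based wording on clinical signs to each intensity grade for subjects who cannot report symptoms.

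Section 12.1 needs no change. The cost is one more CRF field and some definition text, and more events will be labelled related, which the sponsor may find less favourable. Clinical management, endpoints and sample size are unaffected.
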